5.9 Protocol Deviations

The investigator is responsible for complying with all protocol requirements, written instructions, and applicable laws regarding protocol deviations. Protocol deviations are prohibited except when necessary to eliminate an immediate hazard to study subjects. If a protocol deviation occurs (or is identified, including those that may be due to the COVID-19 pandemic), the investigator is responsible

for notifying independent ethics committee (IEC)/independent review board (IRB), regulatory authorities (as applicable), and AbbVie.

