If laboratory samples cannot be obtained, study drug administration may be continued provided the subject has at least 1 post-baseline visit and investigator has reviewed all prior laboratory results and confirms and discusses with the subject that there is no safety concern for the subject to continue use of the study drug in the absence of current laboratory values. Laboratory draws should be obtained as close as possible to the scheduled visit.

Table 3. Clinical Laboratory Tests

Clinical Laboratory Tests			
Hematology	Clinical Chemistry	Other Tests	
Hematocrit	BUN	Central Lab Tests:	
Hemoglobin	Creatinine	Serum pregnancy (beta human chorionic	
RBC count	Total bilirubin	gonadotropin [bHCG]) test	
WBC count	INR (reflex only) ^a	Hepatitis B virus deoxyribonucleic acid	
Neutrophils	Albumin	polymerase chain reaction (HBV	
Bands	ALT	DNA PCR [Per Toxicity Management	
Lymphocytes	AST	Guidelines only])	
Monocytes	Alkaline phosphatase	QuantiFERON-TB Gold	
Basophils	СРК	High-sensitivity C-reactive protein	
Eosinophils	Sodium	(hsCRP)	
Platelet count	Potassium		
Heimaleraia	Bicarbonate/CO ₂	Local Lab Tests:	
Urinalysis	Chloride	Urine pregnancy test	
Specific gravity	Calcium	PPD test / T-SPOT TB	
Ketones	Inorganic phosphorus		
pH Protein Blood Glucose	Uric acid		
Urobilinogen Bilirubin Leukocytes	Total protein		
Nitrites	Glucose		
Microscopic examination, if	Cholesterol		
needed	LDL-C		
	HDL-C		
	Triglycerides		

ALT = alanine aminotransferase; AST = aspartate aminotransferase; BUN = blood urea nitrogen; CO₂ = carbon dioxide; CPK = creatine phosphokinase; DNA = deoxyribonucleic acid; HBV = hepatitis B virus; HDL-C = high-density lipoprotein cholesterol; INR = international normalized ratio; LDL-C = low-density lipoprotein cholesterol; PCR = polymerase chain reaction; PPD = purified protein derivative (tuberculin); RBC = red blood cell; TB = tuberculosis; WBC = white blood cell a. INR will only be measured if ALT and/or AST > 3 × upper limit of normal (ULN).

Pregnancy Tests (Serum and Urine)

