Such an event can result from use of the drug as stipulated in the protocol or labeling, as well as from accidental or intentional overdose, drug abuse, or drug withdrawal. Any worsening of a pre-existing condition or illness is considered an AE. Worsening in severity of a reported AE should be reported as a new AE. Laboratory abnormalities and changes in vital signs are considered to be AEs only if they result in discontinuation from the study drug, necessitate therapeutic medical intervention, meets protocol specific criteria (see Section 6.2 regarding toxicity management) and/or if the investigator considers them to be AEs.

The investigators will monitor each subject for clinical and laboratory evidence of AEs at each visit throughout the study. All AEs will be followed to a satisfactory conclusion.

If any of the following events are reported, then the following supplemental report must be completed (Table 4).

Table 4. Supplemental Electronic Case Report Forms

Adverse Event	Supplemental Form
Cardiac events Myocardial infarction or unstable angina Heart failure Cerebral vascular accident and transient ischemic attack Venous thromboembolism	Cardiovascular (Cardiac) AE eCRF Myocardial Infarction and Unstable Angina AE eCRF Heart Failure Adverse Event eCRF Cerebral Vascular Accident and Transient Ischemic Attack AE eCRF Embolic and Thrombotic Event (Non-Cardiac, Noncentral nervous system [CNS]) eCRF
Herpes Zoster Infection	Herpes Zoster AE eCRF
ALT/AST > 3 ULN	Hepatic Abnormal Laboratory Value Supplemental eCRF Hepatic Supplemental Local Labs eCRF (if applicable) Hepatic Supplemental Procedure eCRF (if applicable)
Serum creatinine > 1.5 × the Baseline value and > ULN Serum creatinine ≥ 2.0 mg/dL	Renal Abnormal Laboratory Value Supplemental eCRF Renal Supplemental Local Labs eCRF (if applicable) Renal Supplemental Procedure eCRF (if applicable)
Creatine kinase (CPK) value ≥ 4 × ULN and no symptoms suggestive of myositis or rhabdomyolysis CPK ≥ 4 × ULN accompanied by symptoms suggestive of myositis or rhabdomyolysis CPK increases considered by the investigator to be an AE	Increased CPK Supplemental eCRF
Acne	Acne eCRF
Death	Death eCRF
Eczema herpeticum (or the synonymous Kaposi's varicelliform eruption)	Eczema herpeticum eCRF

AE = adverse event; ALT = alanine aminotransferase; AST = aspartate aminotransferase; CPK = creatine phosphokinase; eCRF = electronic case report form; ULN = upper limit of normal

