Supplemental study case report forms should be completed in the event of COVID-19 related missed/virtual visits, study drug interruptions or discontinuations, or adverse events (including capture of specific signs/symptoms of infection and testing results).

COVID-19 infections should be captured as adverse events. If the event meets the criteria for a serious adverse event (SAE), then follow the SAE reporting directions per the protocol and above. The following COVID-19 related supplemental eCRFs should be completed (for both serious and non-serious events):

- COVID -19 Supplemental Signs/ Symptoms
- COVID-19 Status Form

If a subject has a confirmed or suspected COVID-19 infection and study drug was interrupted, the investigator should contact the sponsor emergency medical contact listed above before reintroducing study drug.

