8 ETHICS

8.1 Independent Ethics Committee/Institutional Review Board

The protocol, informed consent form(s), recruitment materials, and all subject materials will be submitted to the Independent Ethics Committee/Institutional Review Board (IEC/IRB) for review and approval. Approval of both the protocol and the informed consent form(s) must be obtained before any subject is enrolled. Any amendment to the protocol will require review and approval by the IEC/IRB before the changes are implemented to the study. In addition, all changes to the consent form(s) will be IEC/IRB approved.

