APPENDIX D. ACTIVITY SCHEDULE

The individual activities are described in detail in the Operations Manual (Appendix F). Allowed modifications due to COVID-19 are detailed within the Operations Manual.

Study Activities Table

Activity The activities performed at the Week 24 visit of Study M16-046 will be considered the Baseline activity for Study M19-850 (activities with blue checkmarks in Baseline column only).	Baseline	Week 4	Week 8	Week 16	Week 28	Week 40	Week 52	Unscheduled Visit	PD Visit	30 Days After Last Dose
Visit Window (days)	Ba	±3	±3	±3	± 7	± 7	± 7	Ď	P	±3
□ INTERVIEWS & QUESTION	NAIRI	ES								
Informed consent	*									
Eligibility criteria	✓									
Adverse event assessment	✓	✓	✓	✓	✓	✓	✓	✓	✓	*
Prior/concomitant therapy	✓	✓	✓	✓	✓	✓	✓	✓	✓	✓
Latent TB risk factor questionnaire (annually after last assessment in Study M16-046)					*					
Review pregnancy avoidance recommendations (females of childbearing potential only)	~	>	>	*	*	>	*	*	>	
PROS										
Worst Pruritus NRS	✓	✓	✓	✓	✓	✓	✓	V	✓	
HN-PGIS	✓	✓		✓						
TLOCAL LABS & EXAMS										
Body Weight	✓	✓		✓		✓				
Vital Signs (at FU if needed to monitor AEs)	~	*		✓		✓				*
Physical Exam (at follow-up if needed to monitor AEs)	~									*
Investigator Assessment (EASI, BSA)	✓	✓	✓	✓	✓	✓	✓	✓	✓	
Chest x-ray (annually after last assessment in Study M16-046 if newly positive TB results)					*					
12-Lead ECG					✓					

Activity The activities performed at the Week 24 visit of Study M16-046 will be considered the Baseline activity for Study M19-850 (activities with blue checkmarks in Baseline column only).	Baseline	Week 4	Week 8	Week 16	Week 28	Week 40	Week 52	Unscheduled Visit	PD Visit	30 Days After Last Dose
Visit Window (days)	Bas	±3	±3	±3	± 7	± 7	± 7	Uns	PD	±3
Urine pregnancy test for all female subjects of childbearing age. Monthly home urine pregnancy testing will be performed for visits with > 1 month interval. In case of a positive urine pregnancy test a serum pregnancy test will be performed.	~	~	*	*	*	*	*	*	*	1
TENTRAL LABS										
Clinical chemistry, hematology, urinalysis	✓	~	*	*	*	*	1	*	V	√(only as needed for AEs)
hsCRP	✓	✓	✓				✓	V	✓	
QuantiFERON-TB Gold test (and/or local PPD skin test)					*					
Total serum Immunoglobulin E (IgE)	✓	✓		✓			✓			
Optional Biomarker Sample: Skin biopsy (lesional/non-lesional)	~			*						
Optional Biomarker Sample: Whole blood (DNA/RNA/Serum/Plasma)	~	*		~			1			
R TREATMENT										
Dispense study drug (excluding Week 52)	✓		✓ _	✓ _	✓ _	✓				

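### The emergency clause for dosing without laboratory samples requires a post-baseline visit rather than a result on upadacitinib, and no sponsor contact when consecutive draws are missed

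*Protocol*

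**What the plan says.** Protocol 5.10 (Clinical Laboratory Tests, pandemic modifications) first asks sites to use a local laboratory or other facility where possible. If that fails: "If laboratory samples cannot be obtained, study drug administration may be continued provided the subject has at least 1 post-baseline visit". Two further conditions follow. The investigator must have reviewed all earlier laboratory results, and must give this confirmation in a discussion held beforehand: "there is no safety concern for the subject to continue use of the study drug in the absence of current laboratory values". The paragraph closes: "Laboratory draws should be obtained as close as possible to the scheduled visit".

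Other provisions bear on how this works:

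- **Remote visits.** 5.10 allows visits by phone or video during the pandemic, and 5.8 allows study drug to be shipped to the home.
- **Baseline.** 5.10 takes laboratory Baseline from Week 24 of Study M16-046, before the first dose in this study.
- **Schedule.** The Appendix D row "Clinical chemistry, hematology, urinalysis" is ticked at Baseline, at Weeks 4, 8, 16, 28, 40 and 52, and at unscheduled visits.
- **Monitoring.** 6.1 states: "The investigators will monitor each subject for clinical and laboratory evidence of AEs at each visit throughout the study". 5.8 permits blood collection at home.
- **Sponsor contact.** 5.5 requires it for pandemic dosing delays and asks for it before a subject is discontinued. 6.1 asks for it before restarting drug after a COVID-19 interruption. The missing-samples clause does not mention it.
- **Reporting.** 5.9 requires notification of deviations, including pandemic ones, and 6.1 adds: "Supplemental study case report forms should be completed in the event of COVID-19 related missed/virtual visits".

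**The concern.** The visit is the only objective condition in the clause; the rest is investigator judgement based on earlier results. For a subject who took dupilumab in Study M16-046, every result up to and including Baseline precedes upadacitinib. If the qualifying visit was remote and no sample was taken, the required review contains no information about the study drug.

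Protocol 2.2 lists laboratory changes seen with upadacitinib: raised transaminases, lipids, creatinine and CPK, changes in hemoglobin, and lower white-cell counts. The interruption rules in Table 5 (6.2) are triggered by laboratory values and cannot operate without a sample. Several adverse events of special interest in 6.1, including anemia, neutropenia, lymphopenia and elevated CPK, depend on the same tests.

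The second gap concerns time. A subject who has had on-drug results may still pass consecutive scheduled draws, so that the review rests on ageing values. The closing sentence on timing urges promptness but sets no limit. Sponsor contact is required when pandemic dosing is delayed, yet not when dosing continues without results.

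This concerns subject safety and the completeness of laboratory data. The study does no hypothesis testing, and no sample size or planned analysis depends on it.

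**Working it through.** The plan gives no figure to reproduce. The check is of wording, then of dates and intervals.

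**Can the visit condition be met without an on-drug result?** The clause does not say whether the current visit counts.

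- If it does, the condition is met at every visit from Week 4.
- If an earlier visit is needed, a missed Week 4 draw is not covered, but a remote Week 4 visit qualifies the subject at Week 8.

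On either reading a switched subject can qualify without a sample on upadacitinib. A subject randomized to upadacitinib in Study M16-046 differs: that subject's Week 24 Baseline sample was itself taken after upadacitinib began.

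**Who could be affected under this version?** Inputs: version date 07 January 2021 (Synopsis); interim cutoff 09 March 2021, after all ongoing subjects finish Week 16 (SAP 12.0); visit windows of ±3 days to Week 16 and ±7 days after (Appendix D). Assumption: the cutoff marks completion of Week 16.

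- Latest start: 09 March 2021 − (112 − 3) days = 20 November 2020.
- Least time on study at the version date: 20 November 2020 to 07 January 2021 = 48 days.
- Latest starter's Week 4 window closed: day 28 + 3 = 31, or 21 December 2020, before the version date.
- Latest starter's Week 8 window closed: day 56 + 3 = 59, or 18 January 2021, 11 days after the version date and subject to ethics approval first.

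So the switched-subject case needs Weeks 4 and 8 both missed and not made up. Unless a site had implemented the version by 18 January 2021, Week 16 must then be missed as well.

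**When would a switched subject's first on-drug result come?** Day = 7 × week + window.

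| Draws missed | Next draw | Latest day |
|---|---|---|
| Weeks 4, 8, 16 | Week 28 | 196 + 7 = 203 |
| Weeks 4, 8, 16, 28 | Week 40 | 280 + 7 = 287 |

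**How long can the gap between results be for any subject?** Nominal weeks, windows ignored. With no miss the longest scheduled gap is 12 weeks.

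| Draws missed | Results at | Gap |
|---|---|---|
| Week 28 only | Weeks 16 and 40 | 40 − 16 = 24 weeks |
| Week 40 only | Weeks 28 and 52 | 52 − 28 = 24 weeks |
| Weeks 28, 40 | Weeks 16 and 52 | 52 − 16 = 36 weeks |
| Weeks 16, 28, 40 | Weeks 8 and 52 | 52 − 8 = 44 weeks |

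Both tables assume that no local, home, unscheduled or make-up draw is done. Since the clause has no cap, none of these figures is a maximum.

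**Who still had late draws ahead?** With no approval lag, Weeks 28 and 40 were both still ahead for subjects who started from 07 January 2021 − 196 days = 25 June 2020, up to 20 November 2020. The documents give neither the number of such subjects nor a rate of missed draws.

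**The case against.** The strongest reply is that the clause is a last resort with several layers around it. Local laboratories, home collection, unscheduled tests and make-up draws must all fail before it matters. The investigator can decline to confirm safety when no on-drug result exists. Every scheduled post-baseline visit includes blood work, so a qualifying visit might naturally be read as one with a sample. Protocol 8.2 says that the sponsor will work with sites when emergencies hinder procedures. Protocol 5.5 and Appendix D refer to the Operations Manual for pandemic measures, and a stricter rule may stand there.

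Much of this stands. The layers make the event uncommon, and the manual could not be checked. But local testing applies only if possible, and home visits are optional and depend on local approval. Reading the visit as one with a sample is not secure in a section that itself allows remote visits. The commitment in 8.2 is general and does not require contact before dosing continues. Deviation notices and missed-visit forms record the event but do not require that contact either.

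It is also fair to object that the change below adds a contact trigger and no hard limit, and that one on-drug result of any age would satisfy it. That is accepted: a single missed draw stays with the investigator.

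**Conclusion.** The point holds as a wording gap in Protocol 5.10. The clause requires no laboratory result on upadacitinib, and no sponsor contact before dosing continues through consecutive missed draws. Reach is small for switched subjects and cannot be counted from the documents. For the wider group, the nominal gaps of 24, 36 and 44 weeks show what the wording permits and do not predict what happened.

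Three stronger readings are tempting and are not supported:

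- A reader might infer that switched subjects were commonly dosed without on-drug tests. On the dates above, Week 4 had passed for all ongoing subjects before this version, and nothing supplied shows how many lacked a sample.
- A reader might infer that the sponsor had no oversight. Section 8.2 and the reporting rules show otherwise, and the Operations Manual was not seen.
- A reader might carry the clause into the follow-up to Week 136 described in SAP 2.2. The protocol text for that extension was not supplied, so no count is made.

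The conclusion on reach assumes that the interim cutoff marks completion of Week 16. It says nothing about practice under other protocol versions. Confidence is medium.

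**What to change.** In Protocol 5.10, replace the visit condition with: *at least 1 chemistry and hematology result obtained after the first dose of upadacitinib (in Study M16-046 or Study M19-850)*. Keep the review and confirmation conditions. Add: *If no such result exists, or if samples are missed at consecutive scheduled visits, the investigator must contact the sponsor's medical contact before study drug is continued.* Align the Operations Manual.

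This rewords one sentence and adds one. Subjects randomized to upadacitinib in Study M16-046 who have on-drug results from that study meet the new condition already. A few others would need a sponsor call or a short interruption. Protocol 5.8 sets no time limit on interruption, so that alone would not force withdrawal.

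The formal cost is an amendment, and 8.1 states: "Any amendment to the protocol will require review and approval by the IEC/IRB before the changes are implemented to the study". With up to 150 sites, it is best bundled with the next planned amendment.

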6 SAFETY CONSIDERATIONS

6.1 Complaints and Adverse Events

Complaints

A complaint is any written, electronic, or oral communication that alleges deficiencies related to the physical characteristics, identity, quality, purity, potency, durability, reliability, safety, effectiveness, or performance of a product/device. Complaints associated with any component of this investigational product must be reported to AbbVie.

Product Complaint

A product complaint is any complaint related to the biologic or drug component of the product or to the medical device component(s).

For a product this may include, but is not limited to, damaged/broken product or packaging, product appearance whose color/markings do not match the labeling, labeling discrepancies/inadequacies in the labeling/instructions (e.g., printing illegible), missing components/product, device not working properly, or packaging issues.

Product complaints concerning the investigational product and/or device must be reported to AbbVie within 1 business day of the study site's knowledge of the event. Product complaints occurring during the study will be followed up to a satisfactory conclusion.

Medical Complaints/Adverse Events and Serious Adverse Events

An AE is defined as any untoward medical occurrence in a subject or clinical investigation subject administered a pharmaceutical product and which does not necessarily have a causal relationship with this treatment. An AE can therefore be any unfavorable and unintended sign (including an abnormal laboratory finding), symptom, or disease temporally associated with the use of a medicinal (investigational) product, whether or not the event is considered causally related to the use of the product. In contrast, an adverse reaction (AR) refers to all untoward and unintended responses to an investigational medicinal product at least possibly related to any dose administered.

Such an event can result from use of the drug as stipulated in the protocol or labeling, as well as from accidental or intentional overdose, drug abuse, or drug withdrawal. Any worsening of a pre-existing condition or illness is considered an AE. Worsening in severity of a reported AE should be reported as a new AE. Laboratory abnormalities and changes in vital signs are considered to be AEs only if they result in discontinuation from the study drug, necessitate therapeutic medical intervention, meets protocol specific criteria (see Section 6.2 regarding toxicity management) and/or if the investigator considers them to be AEs.

The investigators will monitor each subject for clinical and laboratory evidence of AEs at each visit throughout the study. All AEs will be followed to a satisfactory conclusion.

If any of the following events are reported, then the following supplemental report must be completed (Table 4).

Table 4. Supplemental Electronic Case Report Forms

Adverse Event	Supplemental Form
Cardiac events Myocardial infarction or unstable angina Heart failure Cerebral vascular accident and transient ischemic attack Venous thromboembolism	Cardiovascular (Cardiac) AE eCRF Myocardial Infarction and Unstable Angina AE eCRF Heart Failure Adverse Event eCRF Cerebral Vascular Accident and Transient Ischemic Attack AE eCRF Embolic and Thrombotic Event (Non-Cardiac, Noncentral nervous system [CNS]) eCRF
Herpes Zoster Infection	Herpes Zoster AE eCRF
ALT/AST > 3 ULN	Hepatic Abnormal Laboratory Value Supplemental eCRF Hepatic Supplemental Local Labs eCRF (if applicable) Hepatic Supplemental Procedure eCRF (if applicable)
Serum creatinine > 1.5 × the Baseline value and > ULN Serum creatinine ≥ 2.0 mg/dL	Renal Abnormal Laboratory Value Supplemental eCRF Renal Supplemental Local Labs eCRF (if applicable) Renal Supplemental Procedure eCRF (if applicable)
Creatine kinase (CPK) value ≥ 4 × ULN and no symptoms suggestive of myositis or rhabdomyolysis CPK ≥ 4 × ULN accompanied by symptoms suggestive of myositis or rhabdomyolysis CPK increases considered by the investigator to be an AE	Increased CPK Supplemental eCRF
Acne	Acne eCRF
Death	Death eCRF
Eczema herpeticum (or the synonymous Kaposi's varicelliform eruption)	Eczema herpeticum eCRF

AE = adverse event; ALT = alanine aminotransferase; AST = aspartate aminotransferase; CPK = creatine phosphokinase; eCRF = electronic case report form; ULN = upper limit of normal

If an AE, whether associated with study drug or not, meets any of the following criteria, it is to be reported to AbbVie clinical pharmacovigilance or contract research organization (as appropriate) as a SAE within 24 hours of the site being made aware of the SAE. Any SAE that has been determined to be at least possibly related to the study drug is defined as a serious AR.

Death of Subject An event that results in the death of a subject.

Life-Threatening An event that, in the opinion of the investigator, would have

resulted in immediate fatality if medical intervention had not been taken. This does not include an event that would have been fatal if it

had occurred in a more severe form.

Hospitalization or Prolongation of Hospitalization An event that results in an admission to the hospital for any length of time or prolongs the subject's hospital stay. This does not include an emergency room visit or admission to an outpatient facility.

Congenital Anomaly An anomaly detected at or after birth, or any anomaly that results in

fetal loss.

Persistent or Significant Disability/Incapacity

An event that results in a condition that substantially interferes with the activities of daily living of a study subject. Disability is not intended to include experiences of relatively minor medical significance such as headache, nausea, vomiting, diarrhea, influenza, and accidental trauma (e.g., sprained ankle).

Important Medical Event Requiring Medical or Surgical Intervention to Prevent Serious Outcome An important medical event that may not be immediately lifethreatening or result in death or hospitalization, but based on medical judgment may jeopardize the subject and may require medical or surgical intervention to prevent any of the outcomes listed above (i.e., death of subject, life threatening, hospitalization, prolongation of hospitalization, congenital anomaly, or persistent or significant disability/incapacity). Additionally, any elective or spontaneous abortion or stillbirth is considered an important medical event. Examples of such events include allergic bronchospasm requiring intensive treatment in an emergency room or at home, blood dyscrasias or convulsions that do not result in inpatient hospitalization, or the development of drug dependency or drug abuse.

[figure not shown]
All AEs reported from the time of study drug administration through 30 days after the last dose of study drug administration will be collected, whether solicited or spontaneously reported by the subject.

Additionally, in order to assist the adjudication process, additional information on any potential major adverse cardiovascular events will be collected, if applicable.

Adverse event information will be collected as shown in Figure 2.

Figure 2. Adverse Event Collection

- * Any AEs occurring prior to the first dose of Study M19-850 should be considered as AEs for Study M16-046, regardless of when the consent form is signed.
- ** Any AEs occurring on or after the first dose of Study M19-850 should be considered as AEs for Study M19-850.

AbbVie will be responsible for Suspected Unexpected Serious Adverse Reactions (SUSAR) reporting for the Investigational Medicinal Product (IMP) in accordance with global and local requirements. A SUSAR is an adverse reaction of which the nature or severity is not consistent with the applicable product information such as investigator's brochure.

Adverse events will be monitored throughout the study to identify any of special interest that may indicate a trend or risk to subjects.

Adverse Events of Special Interest

The following AESI will be monitored during the study:

- Serious infections
- Opportunistic infections
- Herpes zoster
- Active Tuberculosis
- Malignancy (all types)
- Adjudicated Gastrointestinal perforations
- Adjudicated cardiovascular events (e.g., major adverse cardiovascular event [MACE])
- Anemia
- Neutropenia
- Lymphopenia
- Renal dysfunction
- Hepatic disorders
- Elevated CPK

- Adjudicated embolic and thrombotic events (non-cardiac, non-central nervous system).
- COVID-19 (consider while pandemic is ongoing).

Adverse Event Severity and Relationship to Study Drug

The investigators will rate the severity of each AE according to the National Cancer Institute (NCI) Common Terminology Criteria for Adverse Events (CTCAE) version 5.0.

If no grading criteria are provided for the reported event, then the event should be graded as follows:

Mild (Grade 1) Asymptomatic or mild symptoms; clinical or diagnostic observations only;

intervention not indicated

Moderate (Grade 2) Minimal, local or noninvasive intervention indicated; limiting age-

appropriate instrumental activities of daily living (ADL)

Severe (Grade 3 - 5)

Grade 3 Severe or medically significant but not immediately life-threatening;

hospitalization or prolongation of hospitalization indicated; disabling; limiting self care ADL (Self care ADL refers to bathing, dressing and undressing, feeding self, using the toilet, taking medications, and not

bedridden)

Grade 4 Life-threatening consequences; urgent intervention indicated

Grade 5 Death related to AE

The investigator will use the following definitions to assess the relationship of the AE to the use of study drug:

Reasonable Possibility – After consideration of factors including timing of the event, biologic plausibility, clinical judgment, and potential alternative causes, there is sufficient evidence (information) to suggest a causal relationship.

No Reasonable Possibility – After consideration of factors including timing of the event, biologic plausibility, clinical judgment, and potential alternative causes, there is insufficient evidence (information) to suggest a causal relationship.

For causality assessments, events assessed as having a reasonable possibility of being related to the study drug will be considered "associated." Events assessed as having no reasonable possibility of being related to study drug will be considered "not associated." In addition, when the investigator has not reported a causality or deemed it not assessable, AbbVie will consider the event associated.

If an investigator's opinion of no reasonable possibility of being related to study drug is given, an Other cause of event must be provided by the investigator for the SAE.

Pregnancy

While not an AE, pregnancy in a study subject must be reported to AbbVie within 1 working day after the site becomes aware of the pregnancy. Subjects who become pregnant during the study must be discontinued (Section 5.5). If a pregnancy occurs in a study subject or in the partner of a study subject, information regarding the pregnancy will be collected from the date of the first dose through 30 days following the last dose of study drug. The pregnancy outcome will be followed.

In the event of pregnancy occurring in a subject's partner during the study, written informed consent from the partner must be obtained prior to collection of any such information. AbbVie will provide a separate consent form for this purpose.

The pregnancy outcome of an elective or spontaneous abortion, stillbirth or congenital anomaly is considered a SAE and must be reported to AbbVie within 24 hours after the site becomes aware of the event.

Recording Data and Analyses of Safety Findings

Adverse events will be coded using the Medical Dictionary for Regulatory Activities (MedDRA). The number and percentage of subjects with TEAEs (i.e., any event that begins or worsens in severity after initiation of study drug through 30 days after the last dose of study drug will be tabulated by primary MedDRA System Organ Class [SOC] and preferred term [PT]). The tabulation of the number of subjects with TEAEs by severity grade and relationship to study drug also will be provided. Subjects reporting more than 1 AE for a given MedDRA PT will be counted only once for that term using the most severe grade according to the severity grade table and the most related according to the relationship to study drug tables. Subjects reporting more than 1 type of event within an SOC will be counted only once for that SOC.

Reporting Adverse Events and Events of Intercurrent Illnesses

In the event of an SAE, whether associated with study drug or not, the investigator will notify Clinical Pharmacovigilance within 24 hours of the site being made aware of the SAE by entering the SAE data into the electronic data capture (EDC) system. Serious adverse events that occur prior to the site having access to the RAVE® system, or if RAVE is not operable, should be documented on the SAE nonCRF forms and emailed (preferred route) or faxed to Clinical Pharmacovigilance within 24 hours of the site being made aware of the SAE.

Email: [contact]

FAX to: [contact]

For safety concerns, contact the Immunology Safety Team at:

Immunology Safety Team Dept.

[name]

Office: [contact]

Email: [contact]

For any subject safety concerns, please contact the contact listed below:

Primary Therapeutic Area Medical Director EMERGENCY MEDICAL CONTACT

MD, MPH, MBA

AbbVie Inc.

[name]

Contact Information:

Office:
Mobile:
Email:

In emergency situations involving study subjects when the primary TA MD is not available by phone, please contact the 24-hour AbbVie Medical Escalation Hotline where your call will be re-directed to a designated backup AbbVie TA MD:

[contact]

The sponsor will be responsible for SUSAR reporting for the Investigational Medicinal Product (IMP) in accordance with Directive 2001/20/EC.

COVID-19 Pandemic-Related Acceptable Protocol Modifications

Supplemental study case report forms should be completed in the event of COVID-19 related missed/virtual visits, study drug interruptions or discontinuations, or adverse events (including capture of specific signs/symptoms of infection and testing results).

COVID-19 infections should be captured as adverse events. If the event meets the criteria for a serious adverse event (SAE), then follow the SAE reporting directions per the protocol and above. The following COVID-19 related supplemental eCRFs should be completed (for both serious and non-serious events):

- COVID -19 Supplemental Signs/ Symptoms
- COVID-19 Status Form

If a subject has a confirmed or suspected COVID-19 infection and study drug was interrupted, the investigator should contact the sponsor emergency medical contact listed above before reintroducing study drug.

